The main time point for comparison between treatment groups is week 16, but other available measurements at other visits will be analysed as well.

Missing data on the primary and key secondary efficacy endpoints will be imputed using multiple imputation (MI) as the primary imputation method and last observation carried forward (LOCF) as sensitivity analysis. Missing data on all the other secondary efficacy endpoints will be imputed only using LOCF approach.

AEs will be coded according to the Medical Dictionary for Regulatory Activities (MedDRA). The analysis of adverse events will include summary tables displaying counts and percentages of patients experiencing adverse events by system organ class (SOC) and preferred term (PT). If a patient has more than one AE which codes to the same PT, the patient will be counted only once for that PT. The total number of events documented per SOC and PT will also be displayed. All other safety data will be analysed descriptively.

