### **4.5 Discussion of Study Design**

This is a Phase III, multicentre, randomised, double-blind, placebo-controlled study to evaluate the effects of 100 mg safinamide, administered orally once daily (od), in Chinese PD patients, experiencing motor fluctuations while on stable doses of L-dopa (alone or in

combination with other anti-Parkinson drugs). Eligible patients are required to meet the United Kingdom PD Society Brain Bank Clinical Diagnostic Criteria (14).

The double-blind design is adopted to minimize systematic bias in ratings resulting from the knowledge of the treatment received. Randomization helps achieve statistical balance across the two treatment groups. The principal efficacy measure, i.e., the increase in mean daily “OFF” time during the 24-hr diary recording period, was chosen based on regulatory guidance and prior use in other trials in similar populations. Other efficacy measures (“ON” time, UPDRS, CGI, PDQ-39 and NRS) were selected based on the domains of symptoms affected in patients with PD. Tolerability was assessed by changes in laboratory evaluations, vital signs, 12-lead ECG, physical and neurological examinations, and adverse events.

The dose of safinamide (100 mg/day titrated from 50 mg/day after 2 weeks) was selected based on the results of the previous pivotal trials (in particular the study SETTLE), and according to the recommendations of the SmPC. The modulation of glutamate is maximized with the dose of 100 mg. Moreover, this is the dose that has shown to improve significantly dyskinesia (in moderate-severe dyskinetic patients) and PD non-motor symptoms such as chronic pain and mood deterioration. In the SETTLE study, the same dose of 100 mg/day has been administered to a cohort of 168 Asian-Pacific patients, reaching significant positive improvement of fluctuations and motor symptoms.

The study involves a placebo group. Placebo will be added to the standard stabilized treatment as a control of the safinamide group, hence patients on placebo will have benefit from other ongoing anti-PD medication. In addition, patients will be observed during the study more frequently than in the normal clinical practice and in case of any safety issue or lack of efficacy can withdraw from the study at any time.

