#### Treatment Period

At baseline (day 1), eligible patients will enter the treatment period and will be randomised to receive either safinamide (initial 50 mg titrated to 100 mg the day after the Visit 3/week 2, ideally at day 15) or matching placebo, orally od in a 1:1 ratio. The investigational medicinal

product (IMP) will be taken in the morning at breakfast time, in addition to the morning dose of L-dopa and other (if any) PD medications.

Following completion of all baseline assessments, they will receive the first dose of safinamide or placebo (50 mg) at the study centre. The day after the Visit 3/week 2 (ideally at day 15) the dose will be increased at home to 100 mg od. Each patient will receive treatment for 16 weeks, with visits at week 0/day 1 (baseline) and at weeks 2, 6, 10 and 16 (or early termination). A telephone follow-up will be performed 1 week after the end of treatment for safety reasons.

Patients who prematurely withdraw from the study while receiving study medication should complete the early termination visit assessments, when possible.

At the end of the study, the patients will be instructed to contact immediately the Investigator in case of appearance of any adverse reactions. Any ongoing adverse event or clinically abnormal laboratory parameter will be followed until resolution. In addition, all SAEs occurring within 30 days after a patient's last dose of study drug will be followed to their conclusion.

*In the case of intolerable dopaminergic adverse events (AEs), e.g. dyskinesia, it is suggested to decrease the dose of L-dopa by a telephone call as a first step and consider the decrease of the dose of safinamide or placebo from 100 to 50 mg od as a second step. In this second case, patients should undergo an unscheduled visit for safety reasons and maintain the 50 mg dose for the rest of the study. Patients who do not tolerate the 50 mg dose should withdraw from the study and complete the early termination visit assessments, when possible.*

**Efficacy** will be assessed by the changes in "OFF" and "ON" time from the 24-hour patient diary, the Unified Parkinson's Disease Rating Scale (UPDRS), the Clinical Global Impression (CGI), the Parkinson's Disease Questionnaire-39 items (PDQ-39) and the Numerical Rating Scale (NRS).

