### 9.2.2 Visit 3 (Week 2 / Day 14 ± 3 days), Visit 4 (Week 6 / Day 42 ± 3 days) and Visit 5 (Week 10 / Day 70 ± 3 days)

At weeks 2, 6 and 10 (visits 3, 4 and 5), the following assessments and procedures will be performed as indicated in the Study Flow Chart ([Section 29.0, Appendix 1](#)):

- Vital signs (pulse rate, systolic and diastolic blood pressure measured after at least 5 minutes in the supine position).
- Completion of UPDRS, PDQ-39, CGI-S and GCI-C by the rater.
- Completion of NRS by the patient (the night before the visit).
- Recording of concomitant medications and therapies.
- Recording of AEs.
- Review and evaluate daily diary.

- Provide additional daily diary training, as required.
- Issue daily diary at weeks 2, 6 and 10, with instructions to be completed two days before the next visit (weeks 6, 10 and 16).
- Drug accountability.
- Dispense study medication (safinamide or placebo 50 and 100 mg od). Patients will take 100 mg/day safinamide at home in the morning for 14 weeks. In the case of intolerable dopaminergic adverse events (AEs), e.g. dyskinesia, it is suggested to decrease the dose of L-dopa by a telephone call as a first step and consider the decrease of the dose of safinamide or placebo from 100 to 50 mg od as a second step. In this second case, patients should undergo an unscheduled visit for safety reasons and maintain the 50 mg dose for the rest of the study. Patients who do not tolerate the 50 mg dose should withdraw from the study and complete the early termination visit assessments, when possible.

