#### **9.2.3 Visit 6 (Week 16 / Day 112 ± 3 days) / End of Treatment (EOT) / Early Termination (ET)**

Following completion of 16 weeks treatment with safinamide or in the event of premature discontinuation, the following EOT/ET assessments and procedures will be performed as detailed in the Study Flow Chart ([Section 29.0, Appendix 1](#)):

- Physical examination including body weight.
- Vital signs (pulse rate, systolic and diastolic blood pressure measured after at least 5 minutes in the supine position).
- 12-lead ECG in the supine position.
- Completion of UPDRS, PDQ-39, CGI-S and GCI-C by the rater.
- Completion of NRS by the patient (the night before the visit).
- Blood sampling for clinical laboratory assessments (haematology and clinical chemistry).
- Urine sampling for urine (dipstick) pregnancy test for women of child-bearing potential.
- Recording of concomitant medications and therapies.
- Recording of AEs.
- Review and evaluate daily diary.
- Drug accountability.

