### Daily Diary Completion and Assessment

Patients will complete the daily diary by selecting one of the following five options for each 30-minute time period:

- "OFF".
- "ON" without dyskinesia.
- "ON" with non-troublesome dyskinesia.
- "ON" with troublesome dyskinesia.
- Asleep.

If the patients do not know what category applied during a specific 30-minute period, they should be instructed to enter "not done" rather than leaving the time point value blank. During the study visit, the Investigator will review the daily diary with the patient, and the data recorded for each 30-minute period will be transcribed into the eCRF at study centre.

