#### **20.4.4 Handling of missing data**

Missing data on the primary and key secondary efficacy endpoints will be imputed using multiple imputation (MI) as the primary imputation method and last observation carried forward (LOCF) as sensitivity analysis. Missing data on all the other secondary efficacy endpoints will be imputed only using LOCF method. Details regarding the multiple imputation approach (i.e. number of imputations, the randomization seed and the imputation and analysis models that will be used) will be reported in the SAP.

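### The two ON-time endpoints get LOCF only, while OFF time from the same diary gets multiple imputation: a minor mismatch that is cheap to remove

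*Protocol*

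**What the plan says.** Protocol Section 20.4.4 gives the primary and key secondary endpoints "multiple imputation (MI) as the primary imputation method and last observation carried forward (LOCF) as sensitivity analysis". For the remaining endpoints it says "Missing data on all the other secondary efficacy endpoints will be imputed only using LOCF method". The synopsis repeats the rule under Statistical Analysis: "Missing data on all the other secondary efficacy endpoints will be imputed only using LOCF approach". Only the details of the MI (number of imputations, seed, models) are left to the SAP.

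Section 20.2.2 lists total ON time and ON time with no or non-troublesome dyskinesia among the other secondary endpoints. Both come from the primary endpoint's diary: "Patients will complete the daily diary by selecting one of the following five options for each 30-minute time period" (Section 10.1.6). OFF is one option, total ON is three, and the narrower ON endpoint is two of those three; the fifth is asleep. Section 20.4.3.3 gives ON time the same ANCOVA as OFF time.

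On leaving the trial, Section 4.5 says that patients "in case of any safety issue or lack of efficacy can withdraw from the study at any time". Section 9.2.2 adds: "Patients who do not tolerate the 50 mg dose should withdraw from the study and complete the early termination visit assessments, when possible". An early-termination visit is foreseen: "Patients who prematurely withdraw from the study while receiving study medication should complete the early termination visit assessments, when possible". Its list in Section 9.2.3 includes "Review and evaluate daily diary".

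**The concern.** When a week 16 diary is missing, the plan handles the same patient-days in two ways. For OFF time it draws the missing value from a model and carries the uncertainty into the interval. For ON time it freezes the last recorded value and treats it as observed. No reason is given for the difference.

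The two results will be read side by side. Section 4.2.3 already does so for the pivotal trials, where the ON-time result is described as confirmed by the fall in OFF time. Part of any agreement or disagreement between ON and OFF in this trial could therefore come from the imputation method alone. Since the protocol restricts these endpoints to LOCF, an SAP that made MI the main method for ON time would depart from it. This is a choice the protocol has fixed, not a detail left open.

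**Working it through.** **1. The plan's own figures (Section 20.3).** Inputs: 0.9 h, SDs 2.35 and 2.06, 130 per arm, two-sided 0.05, 15% attrition.
- Pooled SD = sqrt((2.35² + 2.06²)/2) = 2.210. SE = 2.210 × sqrt(2/130) = 0.274 h. Power = Φ(0.9/0.274 − 1.96) = 0.907 (0.905 by noncentral t), against the stated 90%.
- 260/0.85 = 306.

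Both reproduce, and neither depends on how ON time is imputed.

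**2. Yardstick.** With 153 per arm, SE = sqrt((2.35² + 2.06²)/153) = 0.253 h. For ON time the SDs and the 0.9 h effect are borrowed from OFF time.

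**3. LOCF expectation, 15% dropout in each arm, unrelated to response, last diary equally often at weeks 2, 6 and 10.** Effect = 0.85 × 0.90 + 0.15 × mean(effect at weeks 2, 6, 10).

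| Assumed effect at weeks 2 / 6 / 10 (h) | LOCF effect (h) |
|---|---|
| 0.9 / 0.9 / 0.9 | 0.900 |
| 0.6 / 0.9 / 0.9 | 0.885 |
| 0.3 / 0.6 / 0.8 | 0.850 |
| 0.1 / 0.3 / 0.6 | 0.815 |
| 0 / 0 / 0 | 0.765 |

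The shift is 0 to 0.135 h. The last row is extreme: no effect through week 10 and the full effect at week 16.

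If a quarter of dropouts have only a baseline diary, which is carried forward, the effect is 0.9 × (0.85 + 0.15 × mean(0, f2, f6, f10)), where f is the fraction of the effect reached at each visit. Linear build-up (2/16, 6/16, 10/16) gives 0.803 h and an early plateau (0.5, 0.8, 0.95) gives 0.841 h: shifts of 0.10 and 0.06 h.

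**4. Poor responders more likely to leave (simulation).** Assumed: 153 per arm, SD of change 2.2, correlation 0.6 between visits, effect 0.3/0.6/0.8/0.9 h at weeks 2/6/10/16, placebo improving 0.5 h, dropout split equally after weeks 2, 6 and 10 with hazard proportional to exp(−0.6z), where z is the standardised last change, and data missing at random. The last column treats ON as the exact mirror of OFF and compares LOCF with MI in the same simulated patients, without early-termination (ET) diaries.

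| Dropout, safinamide / placebo | LOCF, no ET diary | Half have one | All have one | MI | LOCF − MI, same patients |
|---|---|---|---|---|---|
| 15% / 15% | 0.856 | 0.864 | 0.871 | 0.898 | −0.048 |
| 20% / 10% | 0.771 | 0.809 | 0.849 | 0.903 | −0.142 |
| 10% / 20% | 0.938 | 0.912 | 0.887 | 0.899 | +0.040 |

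At balanced attrition 0.05/0.253 = 0.2 standard errors. Only the 15% overall rate stands in the protocol; both unbalanced splits are assumptions.

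**5. True effect zero, 10% / 20%, no ET diaries.** LOCF shows 0.05 to 0.12 h in favour of safinamide. Simulated two-sided false-positive rates were roughly 5 to 6%, up to 7.5% in one run. A normal approximation agrees: 0.05/0.253 = 0.20 gives 5.4%, and 0.12/0.253 = 0.47 gives 7.6%, so the top figure belongs to the largest bias. With ET diaries for half the dropouts the rate was 5.1 to 6.0%, for all 5.0 to 5.3%. With balanced dropout it was 4.6 to 5.2%.

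**6. Interval width.** MI half-width 0.515 h against 0.485 to 0.497 h for LOCF: 0.515/0.497 = 1.036 and 0.515/0.485 = 1.062. In the set-up with baseline carried forward, the SEs at 15% dropout were 0.247 and 0.224 h (linear build-up), ratio 1.10; rounded to 0.25 and 0.22 they give 1.14.

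**The case against.** The rule is deliberate and internally consistent. Synopsis and Section 20.4.4 agree: MI for the two alpha-controlled endpoints, LOCF for those that only support the primary finding (Section 20.4.1) and carry no multiplicity adjustment (Section 20.4.5). OFF time also gets LOCF as sensitivity analysis, so a like-for-like comparison of ON and OFF exists, and OFF by MI against OFF by LOCF shows how far the method moves a diary endpoint in these patients. At balanced attrition the shift is a fraction of a standard error. The larger figures need a dropout split that the protocol does not give, and ET diaries shrink them. Lack of efficacy appears in the placebo rationale, not as a listed reason in Section 15.0.

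All of that stands, and it limits the weight. It does not supply an MI estimate for ON time. The like-for-like comparison is available only under the method that the plan itself ranks second for OFF time, and the ET visit takes place only when possible. The per-protocol analysis and the by-visit summaries do not fill that gap.

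A reader might go further and infer that LOCF favours safinamide. The documents do not support this: the sign depends on which arm loses more patients, and no split is given. Nor does the diary argument reach UPDRS, PDQ-39 or CGI, which are not diary measures.

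**Conclusion.** A cheap improvement of minor weight. The main ON-time and OFF-time analyses rest on different missing-data assumptions although the data come from one diary, and no MI result for ON time is planned. At 15% balanced attrition the method alone accounts for about 0.05 h, or up to 0.10 h if some dropouts have only a baseline diary and the effect builds linearly. Under assumed unbalanced dropout without ET diaries it is about −0.14 h or +0.04 h.

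These sizes borrow the OFF-time SDs and effect. The same-patient comparison also ignores slots marked asleep or not done. MI recovers the true effect here because the simulated data are missing at random; the trial's actual imputation model is for the SAP.

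It would be wrong to read this as an error or contradiction in the protocol, or as a threat to the primary result. The fixed sequence, its type I error, the 306 patients and the power are untouched.

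**What to change.** In Section 20.4.4 and in the synopsis, move the two ON-time endpoints out of the LOCF-only group: *missing ON-time data, for both endpoints, will be handled by MI as for the primary endpoint, with LOCF as sensitivity analysis*. Leave the imputation model to the SAP, including whether OFF and ON are imputed jointly, and leave the other secondary endpoints as they are.

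The cost is one sentence in each place and a little extra programming on data already collected; the LOCF result is kept. ON-time intervals become slightly wider: about 4 to 6% in the main set-up, and about 10% in the set-up with baseline carried forward (14% on the rounded standard errors).

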#### **20.4.5 Multiplicity**

The overall type I family-wise error rate for testing the primary and the key secondary efficacy endpoints will be controlled at the two-sided 0.05 significance level using a Fixed Sequence Procedure (6). Following this procedure, progression to next step will only occurs as long as null hypothesis ( $H_0$ : Active effect = Vehicle effect) from previous step is rejected at 0.05 significance level. The testing procedure is stopped and all the remaining null hypotheses accepted if an acceptance occurs. All individual hypothesis tests will be 2 sided.

1. The first step will test the primary efficacy parameter. The p-value for the null hypothesis must be less than 0.05 to be considered to have met the primary efficacy objective. If the null hypotheses is not rejected (i.e., p-value  $>0.05$ ), the subsequent statistical test (second step) will not be considered statistically significant.
2. The second step will test the key secondary efficacy parameter “change from baseline to week 16 in pain severity, as assessed by an 11-point Numerical Rating Scale”.

For the analyses of supportive secondary efficacy end-points (not key) no adjustment of significance level will be made to account for multiple comparisons.

#### **20.4.6 Multicenter study**

As additional analysis, ANCOVA models for the analysis of primary endpoint and key secondary endpoint described in sections 20.4.3.1 and 20.4.3.2 will be fitted again including the site-by-treatment interaction, in order to test if that interaction is statistically significant, using an alpha=0.1. Also, in order to graphically assess the possible heterogeneity of the treatment effect across centres forest plots will be generated to display the results at each center. In case that the number of patients in each site were scarce, sites will be gathered into “region”. Upon completion of the study and prior to unblinding, study statisticians in consultation with the clinical team will determine the pooling based on enrolment numbers and geographical proximity.

#### **20.4.7 Interim Analyses**

No interim analyses are planned.

#### **20.4.8 Safety data**

All safety endpoints will be summarized and analyzed using the Safety Population.

#### Incidence of Treatment Emergent Adverse Events

The number and the percentage of patients reporting TEAEs, treatment emergent SAEs, severe TEAEs, TEAEs leading to discontinuation and TEAEs leading to death will be presented by treatment group, along with the number of events occurring.

TEAEs will be summarized also by System Organ Class and Preferred Term according to MedDRA; they will be additionally summarized by severity and relationship to treatment. A separate summary table will be provided for SAEs.

Only TEAEs, i.e. events with an onset date on or after the date of IMP start, will be included in the summary tables. Individual data listings will include all AEs recorded; a separate listing will be provided for treatment-emergent SAEs.

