## 17.8 Adverse Event Reporting

The Investigator must report to the CRO all AEs which occur during the study following written informed consent, regardless of their relationship to IMP. All AEs are to be recorded by the Investigator on the AE information page of the eCRF. For SAEs information must be recorded also on the "Adverse Event Form for immediate reporting".

In addition, an SAE will have to be reported according to the following detailed procedure.

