### **9.1.1 Visit 1 - Screening Visit (Day -14/-2)**

The following assessments and procedures will be performed as detailed in the Study Flow Chart ([Section 29.0, Appendix 1](#)):

- Obtain written informed consent ([Section 21.0](#)).
- Assignment of unique screening number; numbers will be allocated in sequence within each study center.
- Check of inclusion and exclusion criteria ([Sections 8.2.1 and 8.2.2](#)).
- Recording of demographic data, including age, sex, ethnicity, smoking and alcohol use ([Section 10.1.1](#)).
- Recording of medical history and PD diagnosis using the United Kingdom Parkinson's Disease Society Brain Bank ([Section 29.0, Appendix 2](#)), including Hoehn and Yahr (20) stage ([Section 29.0, Appendix 3](#)).
- Physical examination including height and body weight ([Section 10.1.2](#)).
- Neurological examination ([Section 10.1.2](#)).
- Vital signs (pulse rate, systolic and diastolic blood pressure measured after at least 5 minutes in the supine position) ([Section 10.1.3](#)).
- 12-lead ECG in the supine position ([Section 10.1.4](#)).
- Daily diary training ([Section 10.1.6](#)).
- Blood sampling for clinical laboratory assessments (haematology and clinical chemistry, including liver function tests) ([Section 10.1.5](#)).
- Urine sampling for urine (dipstick) pregnancy test for women of child-bearing potential ([Section 10.1.5](#)).
- Recording of prior medications, concomitant medications and therapies ([Section 11.0](#)).
- Recording of AEs which occur following written informed consent ([Section 17.0](#)).
- Issue daily diary with instructions to be completed two days before the baseline visit (visit 2).
- Issue NRS to be completed the night before the baseline visit (visit 2).

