### 10.1.7 Safety Evaluations

Safety will be assessed throughout the study, i.e. from the provision of informed consent until the last patient visit. In addition, any AE that, in the opinion of the Investigator, requires the patient to withdraw from treatment or from the study, will be followed until the event has subsided or the condition has stabilised. All SAEs that are spontaneously reported within 30 days of a patient's last dose of study drug will also be reported and followed.

Individual safety assessments will be performed using the parameters and time points for collection listed below:

- Physical examination, clinical chemistry and haematology and 12-lead ECG at screening (visit 1) and week 16 (visit 6/EOT/ET).
- Neurological examination at screening (visit 1).
- Vital signs at each study visit AEs at every post-screening visit.

Further details are provided in [Section 10.1](#) and in the Study Flow Chart ([Section 29.0, Appendix 1](#)).

Further information regarding AE definitions and reporting is provided in [Section 17.0](#).

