## **17.0 REPORTING SAFETY INFORMATION**

### **17.1 Definition of Adverse Event (AE)**

An Adverse Event (AE) is "*any untoward medical occurrence in a patient or clinical trial subject administered a medicinal product and which does not necessarily have a causal relationship with this treatment*".

Adverse events include:

- Worsening (change in nature, severity or frequency) of conditions present at the onset of the study.
- Patient deterioration due to the primary illness.

- Intercurrent illnesses.
- Drug interactions.
- Events related or possibly related to concomitant medications.
- Abnormal laboratory values, as well as significant shifts from baseline within the range of normal, which the Investigator considers to be clinically significant.

An AE can therefore be any unfavourable and unintended sign (including an abnormal laboratory finding), symptom, or disease temporally associated with the use of an IMP, whether or not considered related to the IMP.

The following medical conditions will not be documented as AEs and will be documented as medical history (or other as applicable):

- Symptoms or laboratory or instrumental abnormalities of a pre-existing (i.e. before patient entered the study) condition which have not worsened since enrolment;
- Surgical interventions or hospitalizations planned before patient entered the study.

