ECG: electrocardiogram; UPDRS: Unified Parkinson's Disease Rating Scale; CGI-S: Clinical Global Impression-Severity; CGI-C: Clinical Global Impression-Change; PDQ-39: Parkinson's Disease Questionnaire-39 items; NRS: Numerical Rating Scale.

1. Subjects who prematurely withdraw from the study while receiving study medication should complete the EOT Visit assessments, when possible.
2. Neurological examination at screening visit only.
3. Details of excluded and permitted concomitant treatments are presented in Section 11.0 of the protocol.
4. The diary should be completed by the subject two days before the baseline visit and the visits at weeks 2, 6, 10 and 16 (visits 3,4,5 and 6) for recording of "OFF" and "ON" time
5. To be evaluated at approximately the same time of day as at the baseline visit, if possible at least 1 hour after the subject has taken their morning dose of safinamide and is in the optimal "ON" state.
6. NRS will record PD pain intensity in the evening before going to sleep prior to the baseline visit and the visits at weeks 2, 6, 10 and 16 (visits 3,4,5 and 6), as the worst pain experienced in the past 24 hours (at any time during the day). If the patient suffers for more than one pain, the more severe pain must be recorded.
7. All women of child-bearing potential.
8. The Investigator must report all AEs which occur during the study following written informed consent.
9. The first dose of safinamide or placebo (50 mg once daily) will be administered at the study centre. The dose of safinamide or placebo will be titrated the day after the Visit 3/week 2, ideally at day 15 at home to 100 mg once daily. See Section 7.0 of the protocol.

## APPENDIX 2

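### The TEAE definition in section 20.4.8 uses onset date alone, so an adverse event that starts in screening and worsens or turns serious on study drug can be left out of the AE summary tables

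*Protocol*

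**What the plan says.** Section 20.4.8 (current version, 2.0) fixes which events are tabulated: "Only TEAEs, i.e. events with an onset date on or after the date of IMP start, will be included in the summary tables". The tables concerned are the counts of TEAEs, treatment-emergent SAEs, severe TEAEs and TEAEs leading to discontinuation or death, and the breakdowns by system organ class, preferred term, severity and relationship. An SAE table is also planned, "A separate summary table will be provided for SAEs", but the TEAE restriction follows it directly and applies to the summary tables as a whole. Events outside the definition are kept only as follows: "Individual data listings will include all AEs recorded; a separate listing will be provided for treatment-emergent SAEs".

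Collection starts earlier than the tables do. Section 17.8 says: "The Investigator must report to the CRO all AEs which occur during the study following written informed consent, regardless of their relationship to IMP". The Visit 1 list in section 9.1.1 has "Recording of AEs which occur following written informed consent", and the flow chart footnote repeats the duty: "The Investigator must report all AEs which occur during the study following written informed consent". Section 17.8.1 makes SAEs reportable from consent as well. One leftover phrase in section 10.1.7 points the other way: "Vital signs at each study visit AEs at every post-screening visit".

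Section 17.1 lists among adverse events: "Worsening (change in nature, severity or frequency) of conditions present at the onset of the study".

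**The concern.** Treatment emergence is normally meant to cover two kinds of event: those that first appear after dosing starts, and those already present that get worse afterwards. The rule here covers only the first. Since AEs are recorded from consent and screening runs from Day -14 to Day -2, there is a defined class of events with a known onset before the first dose. If study drug aggravates one of these, the tables that serve the safety objective may not show it.

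TEAEs and treatment-emergent SAEs are the first-listed safety endpoint in section 20.2.3, and section 5.2 sets comparison with placebo as the safety objective. If safinamide does aggravate ongoing events, leaving them out would narrow the visible difference between the arms.

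**Working it through.** The protocol gives no figure to reproduce, and the point involves no formula. The check is to apply the 20.4.8 rule (onset date on or after the date of first IMP intake) to each type of event, together with 17.1.

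1. **Condition present before consent that worsens on treatment.** Section 17.1 makes the worsening an AE, and only pre-existing conditions that have not worsened stay in medical history. If the AE is dated at the worsening, it is a TEAE and is tabulated.
2. **AE starting after consent and before Day 1 that worsens on treatment.** Kept as one record with its original onset, it is not a TEAE and is absent from every AE summary table. Recorded again with the date of worsening, it is a TEAE. Neither 17.1 nor 17.7 says which applies.
3. **The same AE becoming serious on treatment.** The worsening item in 17.1 names nature, severity and frequency, but not seriousness. With its original onset the event is missing from the treatment-emergent SAE counts, the SAE table and the treatment-emergent SAE listing. It remains in the all-AE listing.
4. **AE on Day 1 before the first dose.** Section 9.2.1 places the first dose at the centre after the relevant visit procedures. The onset date equals the IMP start date, so the event is counted as treatment-emergent.
5. **Partial or missing onset date with unclear status.** The missing-data paragraph of 20.4.8 counts it as treatment-emergent. This does not help cases 2 and 3, where the date is known.

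Cases 1 and 2 may be clinically identical and differ only in whether onset fell before or after consent, yet one is tabulated when dated at the worsening and the other depends on how the site records it, across about 35 centres.

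**Size.** The number affected is the number of patients with a screening AE ongoing at first dose, multiplied by the proportion whose event then worsens or turns serious. The protocol gives neither quantity. Purely for scale, I assume that 5% to 10% have such an AE and that 10% to 25% of these worsen:

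- Both arms: 306 × 0.05 × 0.10 = 1.5 to 306 × 0.10 × 0.25 = 7.7 patients.
- Per arm: 153 × 0.05 × 0.10 = 0.8 to 153 × 0.10 × 0.25 = 3.8 patients.

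These rates have no anchor in the document, and they include worsening from natural course. They show only that the count is likely to be small.

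**The case against.** The strongest reply is that no loss has been shown. The list in 17.1 is illustrative, and the governing definition covers any untoward occurrence, which would take in aggravation of a screening AE. If sites record that aggravation as a new event with its own date, the existing rule tabulates it. On this view the gap is an eCRF completion convention, which may well be in a document not shown here. This stands in part: the omission depends on the event keeping its original onset date. It does not remove the point, because the protocol itself fixes the TEAE definition, gives no new-record or onset-date rule, and does not list seriousness as a form of worsening. A SAP that followed the text would inherit the gap, and one that added a worsening clause would depart from the protocol.

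A reader might infer more than the documents support:

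- **That such events are certain to be lost.** Nothing says that they keep their original date.
- **That all safety tables are affected.** Laboratory, vital-sign, physical examination and ECG summaries do not use the TEAE rule. The all-AE listing retains the event, and an SAE is still reportable within 24 hours.
- **That version 2.0 created the mismatch by moving collection back to consent.** Section 17.8 of version 1.0 already required this; version 2.0 added it to Visit 1 and the flow chart.
- **That the Day 1 rule biases the comparison.** Events before dosing cannot be caused by the drug, and with 1:1 double-blind allocation they are expected to fall equally on both arms. Over-inclusion is also in line with the rule for unclear dates.

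**Conclusion.** The point holds in conditional form. As written, section 20.4.8 leaves out of all AE summary tables an event that starts between consent and first dose and worsens or becomes serious on IMP, provided that it keeps its original onset date. The protocol does not settle that proviso. The case of an event turning serious is the clearest, because 17.1 does not address it. Counting pre-dose Day 1 events is a minor imprecision.

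The number of patients cannot be derived from the document and is probably small. The correction is still worth making, because a single missing case can matter in tables of SAEs, discontinuations and deaths. No efficacy result, alpha level or power figure is affected.

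**What to change.** - **Section 20.4.8:** define a TEAE as an AE with onset at or after the first IMP intake (using date and time, or a pre-dose flag, for Day 1), or an AE or condition present before that intake which increases in severity or frequency, or becomes serious, afterwards.
- **Section 17.7:** state that such worsening is recorded as a new AE dated at the worsening, and carry this into the eCRF completion instructions. The new record, not the original one, should enter the tables, so that the event is counted once.
- **Section 10.1.7:** align the phrase on post-screening visits with section 9.1.1 and the flow chart, which start AE recording at consent.

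The cost is a few sentences in the protocol, matching text in the SAP and an eCRF note. The downside is slightly more AE records and possibly higher AE counts.
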